2. Stage-appropriate treatment rate;
3. Patient, caregiver, and provider satisfaction with the care provided;
4. Patient and caregiver quality of life;
5. Patient and caregiver perception of their inclusion in the decision-making process;
6. Survival

In an exploratory sub-aim, we will use the retrospective and prospective data generated from the routine delivery of care to lung cancer patients within the Baptist Healthcare System to develop computer simulation models of the flow of care (process engineering) to examine the most efficient pathways of care. By these means, we will critically evaluate the pattern, quality and efficiency of care within our healthcare system, using patient-centered and other stakeholder-relevant endpoints.

Research setting

Clinical care will take place within the Baptist Memorial Health Care system (Memphis metro, DeSoto County, MS, NEA Jonesboro, Oxford, MS and Golden Triangle) and data abstraction will take place at the Baptist Cancer Center in Memphis, TN. Patient, caregiver, and physician surveys for feedback will be administered by trained personnel within the research group, supplemented (as necessary) by a HIPAA-compliant professional survey company pre-approved by the administration of the Baptist Memorial Healthcare Corporation. All data analyses will be performed by statisticians at the University of Memphis, School of Public Health, using coded, de-identified, anonymized patient, caregiver, and provider data. The process engineering sub-aim will be performed by [name] at the University of Wisconsin - Madison using anonymized, coded, de-identified patient data.

Main outcomes to be measured

The main outcomes to be measured are measures of implementation success, quality of care and outcomes of care. Specifically, the outcomes are patient, caregiver, and clinical provider satisfaction

scores, patient and caregiver quality of life, timeliness of care, completeness of staging, surgical resection rate, stage-appropriate treatment rate, and survival.

Methods or procedures

This study will evaluate the quality of care received within the healthcare system by using the Reach, Effectiveness, Adoption, Implementation and Maintenance (RE-AIM) framework. We will use a combination of quantitative data analysis, computer simulation modeling, and analysis of survey responses to address the different components of the RE-AIM framework.

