used, psychometrically sound, 37-item, multidimensional instrument that includes five sub-scales. Sub-scales assess physical, functional, social, and emotional domains of QOL plus lung cancer-specific symptomatology. The FACT-L has demonstrated reliability, validity, and sensitivity to within-person change (Browning et al., 2009; Cella et al., 1993, 1995, 2002; Paull et al., 2006). It is written at the 4th grade reading level, has been validated for use with special populations such as older adults and those living in rural areas, and has demonstrated equivalence in mode of administration (interview vs. self-administration).

Patient depression and anxiety will be measured with the Hospital Anxiety and Depression scale (HADS; Zigmond and Snaith, 1983), a widely used 14-item instrument to evaluate depression and anxiety in clinical populations. It was created specifically to avoid reliance on aspects of depression and anxiety that are also common somatic symptoms of illness, such as fatigue and sleep difficulties. The HADS has been extensively validated in both clinical and non-clinical populations (Bjellanda et al., 2002; Trask et al., 2004).

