3. Provider satisfaction scores corresponding to a 5 or 6 on a 6-point Likert-type scale (very satisfied or satisfied, respectively) in >70% of providers in surveys administered after each provider's active

interaction with the clinical program, either by direct participation (for participating providers) or after referring 5 patients into the program (for non-participating providers).

Certain multidisciplinary clinic staff (clinical research professionals) will be assigned with administering these surveys. These clinical research professionals will meet with patients during their initial visit to the Multidisciplinary clinic for the purpose of consenting patients to participate in the survey administration arm of the study and possibly to participate in the prospective comparative effectiveness study (Specific Aim #3). Once a patient/caregiver dyad gives consent to participate, surveys will be administered up to three times – once near the beginning of contact with the multidisciplinary clinic, a second time after a c. 3 month interval, and a third time after another c. 3 month interval (c. 6 months from the initial baselines survey). For clinical providers, surveys will be administered three times – once near the beginning of contact with the multidisciplinary clinic, and then two more times at 6 month intervals (after 6 and 12 months). Every attempt will be made to administer surveys to patients, caregivers, and clinical providers in person. If that is not possible, surveys may be taken over the phone, or by mail, but only if necessary. Patient dyads will be compensated with a \$10 Kroger gift card upon successful completion of the last round of surveys. Caregivers and clinical providers will not receive any financial compensation.

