Models for survival events: All patients will be followed up for at least one year from the beginning of the study (with a median of 1.5 year). The follow up time will be longer if the starting time is retrospectively tracked back to the date of first imaging diagnosis. Assuming t_i represents the time (days) from the first imaging diagnosis to death, $h(t_i)$ is the corresponding hazard function, the proportional hazard model is $\text{log}(h(t_i)) = \beta * G_i + \gamma X_i$. The exponent of β is the hazard ratio of survival between multidisciplinary program and controls. In addition, the proportional hazard assumption in the model will be examined visually by plotting - $\text{log}(\text{log}(\text{survival}))$ and time, and also by statistically testing by adding time interaction in the model. We will also visually compare the survival curve difference using Kaplan-Meier estimate and log rank test for curve difference between two groups. Finally, the Fine-Gray competing risk model will be used to compare lung cancer specific death.

Analyses for self-reported satisfaction with care and quality of life: patient, caregiver, and provider satisfaction scores are measured using survey methods. Surveys also are used to measure quality of life, including health related quality of life and depression/anxiety (in patients and caregivers) and caregiver burden (in caregivers only). For each measure, summary scores will be calculated according to the instructions in each survey instrument. Although the scores based on Likert scales can be treated as continuous variables, we will dichotomize the satisfaction scores as satisfactory (scores 5-6 on a 6-point scale) and unsatisfactory (scores 1-4), to correspond to our benchmark criteria. Descriptive analysis and logistic model similar to the previous analyses will be used.

Potential benefits to subjects/others.

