### **Statistical Methods (Supplemental)**

The study was designed with overall survival as the primary endpoint. The design provided 80% power, with alpha of 0.05, to detect a hazard ratio of 1.25 between patients receiving multidisciplinary care and serial care. We targeted enrollment of 150 patients on the multidisciplinary arm and 300 patients on the serial care arm, matched by clinical stage (based on the initial diagnostic CT scan), performance status, insurance status, race, and age range. After initiation of the study, it was determined that the individual 1:2 matching strategy was not attaining high level matches within the allotted parallel time frame for the required number of subjects. To accommodate this change the following revisions were made to the statistical methodology. A frequency matching strategy was used based on the matching variables (age, sex, and histology were controlled for as a model covariate for better numerical efficiency). Crude comparisons between groups were made using standard univariate two sample methods. Comparative analyses were then conducted using matching variables as strata, per original design, with the strata now allowing multiple cases and controls per match group (frequency matching). Specifically, analyses were designed based on conditional logistic regression for each binary endpoint and stratified cox proportional hazards models for survival endpoints. Models were further adjusted to include age, sex, and histology in addition to the adjustment for strata described above. For each outcome, additional statistical models were evaluated controlling for matching variables as covariates in unconditional analyses. All analyses were conducted in SAS Version 9.4 (Cary, NC) with a type-I error rate of 0.05.

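### The quality-of-life paragraph offers only a logistic model, and the plan does not commit to adjusting for the baseline score it collects

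*Protocol*

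**What the plan says.** The protocol's Study design section lists "Patient and caregiver quality of life" among the endpoints of the comparative study. Under Methods or procedures (Effectiveness), patients complete FACT-L and HADS; caregivers complete SF-36, HADS and a burden scale. FACT-L is supported partly on this ground: "The FACT-L has demonstrated reliability, validity, and sensitivity to within-person change". Surveys are given up to three times: once near the start of contact with the multidisciplinary clinic, "a second time after a c. 3 month interval, and a third time after another c. 3 month interval".

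One paragraph in the protocol's Statistical analysis section covers satisfaction and QOL together. It says "For each measure, summary scores will be calculated according to the instructions in each survey instrument", then "we will dichotomize the satisfaction scores as satisfactory (scores 5-6 on a 6-point scale) and unsatisfactory (scores 1-4"), and ends with "Descriptive analysis and logistic model similar to the previous analyses will be used". The logistic model it points back to contains care group and a set of other confounders that are not named.

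The SAP (Statistical Methods (Supplemental)) specifies "conditional logistic regression for each binary endpoint and stratified cox proportional hazards models for survival endpoints", adjusted for the matching strata, age, sex and histology. It adds, for each outcome, unconditional models with the matching variables as covariates. It does not mention QOL or a baseline score.

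**The concern.** A logistic model needs a binary outcome. The only cut-off in the paragraph belongs to a 6-point satisfaction scale and cannot be carried over to FACT-L, HADS, SF-36 or the burden scale. If QOL does go to that model, the cut-off is still to be chosen, possibly with the data in view. If it does not, no adjusted model for a continuous QOL score is written down.

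The second issue is the baseline score. Care model is not assigned at random, and the protocol's Reach component itself asks which kinds of patient come to the multidisciplinary clinic. Patients of the same stage and performance status may still start with different QOL. Where that happens, a follow-up comparison that ignores the starting score credits part of the difference to the care model. It also discards precision already paid for by collecting the baseline survey.

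**Working it through.** The documents give no QOL effect size, SD, power or sample size, so there is no planned QOL figure to reproduce. The check has three parts.

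**1. Where could a baseline score enter?**
- Matching variables (protocol, Eligibility criteria): stage, performance status, insurance, race, age range. No QOL variable.
- Protocol logistic model: other confounders, not named. Baseline is permitted but not required.
- SAP covariates: strata, age, sex, histology. Baseline is not named.
- SAP additional models: matching variables only.
- Protocol trend analysis: follows quality-of-care outcomes over the study period, not QOL within patients.

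**2. What could ignoring baseline cost?** From the documents: 150 v. 300 patients, two-sided alpha 0.05 (stated for survival), and a 60% response benchmark, giving 90 v. 180. That benchmark was set for satisfaction responses after contact with the multidisciplinary program, so it serves here only as a completeness scenario. Assumed: baseline gap d0 = 0.2 SD, baseline-to-follow-up correlation r = 0.5 to 0.7, no true effect of care.
- Bias in an unadjusted follow-up comparison = r × d0 = 0.10 to 0.14 SD.
- SE = √(1/90 + 1/180) = 0.129 SD; at full size √(1/150 + 1/300) = 0.100 SD.
- False-positive rate = Φ(bias/SE − 1.96) + Φ(−bias/SE − 1.96).

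| Comparison, d0 = 0.2 SD | r = 0.5 | r = 0.7 |
|---|---|---|
| Continuous, 90 v. 180 | 12.1% | 19.2% |
| Continuous, 150 v. 300 | 17.0% | 28.8% |
| Split at control median, 90 v. 180 | 9.5% | 13.9% |

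If matching halves the gap to 0.1 SD, the continuous figures at 90 v. 180 fall to 6.7% and 8.4%. In a simulation at 150 v. 300 with r = 0.6 and d0 = 0.2 (2,000 runs), adding baseline as a covariate brought the rate from 22.5% to 5.1%.

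Precision: baseline adjustment multiplies the residual variance by 1 − r², that is 0.75 to 0.51, a cut of 25% to 49%. For an assumed true difference of 0.3 SD at 90 v. 180, power is 41% to 45% dichotomised (cut at the control group's top 20% to 50%), 64% continuous without baseline, and 77% to 90% with it.

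**3. How many patients die before the 6-month survey?** The protocol's Sample size calculation gives one-year mortality of 15%, 30% and 50% for stage I/II, III and IV, with a stage mix of 30%, 30% and 40%. With constant hazard within stage, 6-month mortality is 1 − √(1 − m):

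0.3 × 0.078 + 0.3 × 0.163 + 0.4 × 0.293 = 0.190, about 19%.

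This treats the mortality clock as starting near the first survey, which the documents do not state.

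**The case against.** A reader might infer that QOL is confined to crude two-sample tests. The documents do not support that. The SAP's additional models apply to each outcome, and the protocol's Statistical analysis section says modelling adjusted for measured confounders will be the main tool. Nor is it certain that QOL goes to the logistic model: the preceding sentence dichotomises satisfaction only, so the logistic model may be meant for satisfaction alone. Even so, the SAP's additional models control for matching variables, not the starting score, and the ambiguity itself needs settling.

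A reader might also infer that the comparison is confounded, or that the plan excludes the baseline score. Neither is shown. The protocol's open set of confounders could hold a baseline score, and matching on stage and performance status should remove part of any gap. What stands is that nothing commits the analysis to baseline adjustment.

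The proposed remedy is also open to challenge. The first survey is tied to contact with the multidisciplinary clinic, and consent is sought during the initial visit, so it may follow first exposure. Serial patients are approached only after a matching patient consents, and their baseline timing is not defined. Adjustment may also fall short. If a 0.2 SD gap were stable rather than fading by the factor r, the adjusted model would keep a bias of 0.2 × (1 − r) = 0.06 to 0.10 SD, a false-positive rate of about 10% to 15% at 90 v. 180. The unadjusted comparison would then carry the full 0.2 SD (0.2/0.129 = 1.55, about 34%). Adjustment is still better, but baseline must be defined first.

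Finally, overall survival is the primary endpoint, no power is claimed for QOL, and part of the SAP text was unavailable, so absence is judged on what could be read.

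**Conclusion.** The point holds as a cheap improvement. The QOL paragraph gives a logistic model without a QOL cut-off, and neither the protocol's models nor the SAP's named covariates include the baseline score. The QOL comparison is therefore left open to confounding by starting QOL, and it loses precision.

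The size is illustrative. The rate of 12% to 19% rests on an assumed 0.2 SD gap, an assumed correlation of 0.5 to 0.7, 60% completeness in both groups and an unadjusted continuous test. It is not an estimate of this trial's error rate. The power gain likewise depends on an assumed 0.3 SD effect. Only the figure of about 19% dead by 6 months comes from the plan's own rates, with the constant-hazard assumption added.

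**What to change.** Amend the SAP as follows:
- **Define baseline** in the same way for both groups, for example by time from diagnosis and before treatment starts. Report a sensitivity analysis limited to baseline surveys completed before treatment.
- **Model each QOL, HADS and burden score as continuous**, in a repeated-measures linear model of the 3- and 6-month scores on care model, time and care-by-time. Adjust for the same instrument's baseline score, the matching factors, age, sex and histology.
- **Confine the logistic model to satisfaction**, or state and justify a cut-off in advance for any other score.
- **State that 6-month results are among survivors**, and name a sensitivity analysis for deaths before the survey. The choice of method, and of a main instrument and time point, is for the study team.

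Cost: SAP wording and one further model on data already collected. Patients without a baseline survey need imputation or drop out. Adjustment may not remove all of a starting difference, and may remove a little early effect if the first survey follows the clinic visit. The SAP text is written in the past tense, so the revision should record whether these choices were made before the QOL data were seen.

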Patient feedback will be obtained on (a) satisfaction with care, and (b) quality of life (QOL), including both health-related QOL and depression/anxiety. Patient satisfaction will be measured using existing measures and measures created specifically for this study. The existing measure was originally developed for the Consumer Assessment of Healthcare Providers and Systems (Hays et al., 1999) and used in the Cancer Care Outcomes Research and Surveillance (CanCORS) Consortium (Ayanian et al., 2004; 2010), and assesses the interpersonal aspects of cancer care. Its 13 items load on three factors, including physician communication (e.g., “How often did your doctors listen carefully to you?”), nursing care (e.g., “How often were your nurses as helpful as you thought they should be?”), and coordination and responsiveness of care (e.g., “How often did the doctors, nurses, and other medical staff providing your care seem to work well together as a team?”). The three factors have been shown to have good internal consistency (Cronbach’s alphas ranging from 0.84-0.86 for the three factors for both lung cancer patients and surrogate respondents (family members) (Ayanian et al., 2010). We also will use single items from CanCORS to assess overall rating of care (“Overall, how would you rate the quality of your health care since your diagnosis of cancer?”) and perceived relative quality of care (“Would you say that you received medical care that was better than, about the same as, or worse than other patients with lung cancer?”). In addition, we developed items to tap aspects of satisfaction related to specific outcomes of this project, including satisfaction with the timeliness of care (e.g., “How satisfied are you with the length of time between learning that you might have cancer to being diagnosed?”), perceived obstacles to completing treatment, and perceived quality of care from specific care team members (e.g., oncologist, nurse navigator).

Patient QOL will be measured using two validated instruments. Health-related QOL will be measured with the Functional Assessment of Cancer Therapy – Lung Cancer (FACT-L) scale. The FACT-L is a widely

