We also will collect data on satisfaction with care and quality of life for the main informal caregiver (defined as the person who gives the patient the greatest amount of assistance and care on a day-to-day basis) for each patient who is enrolled in the study. Satisfaction measures will parallel the measures used with patients (described above). Caregiver health-related QOL will be assessed using the Short Form (36) Health Survey (SF-36; McHorney et al., 1994). The SF-36 is a widely used and validated measure of health-related QOL. It contains 36 questions and yields a psychometrically-based profile of physical and mental health in eight areas, including vitality, physical functioning, bodily pain, general health perceptions, physical role functioning, emotional role functioning, social role functioning, and mental health. The SF-36 has been validated in a number of populations, including caregivers (Bell et al., 2001, Machnicki et al., 2009) and is sensitive to change among clinical groups over time (Hemingway et al., 1997). Depression and anxiety will be assessed with the HADS, which also will be administered to patients (described above). Lastly, caregiver burden will be assessed using the Brief Assessment Scale for Caregivers of the Medically Ill (Glajchen et al., 2005), a validated 14 item scale that taps both negative (e.g., distress, lack of time) and positive (e.g., making the relationship with patient closer) aspects of caregiving.

For clinical provider feedback, we will use 2 instruments. The first instrument assesses provider satisfaction, focusing on the stated benchmarks of this study. It was developed specifically for this study, based on published surveys of provider experiences delivering cancer care (Taylor et al., 2012a, 2012b, Patkar et al., 2011; Shulman et al., 2013). The second survey is a multidisciplinary care workforce and workflow survey that seeks to identify obstacles to institutional multidisciplinary care.

The specified program benchmarks for survey administration and responses are as follows:

1. Ability to get satisfaction score responses from 60% of patients, caregivers and providers after interaction with the multidisciplinary care program;
2. Patient satisfaction scores corresponding to a 5 or 6 on a 6-point Likert-type scale (very satisfied or satisfied, respectively) in >80% of patients in surveys administered after initial clinic evaluation;

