The above sample size estimate is based on our preliminary data. Among eligible patients, about 30% of cases are stage I/II, 30% stage III, and 40% stage IV. The corresponding one year mortality rates are 15%, 30% and 50%, respectively, and two year mortality rate is 30%, 50% and 70% respectively. Thus we estimated the range of the mortality rates from 30% to 50% in our mixed sample with a median follow up of 1.5 years. Furthermore, we estimate the relative difference in survival 20%-30% (i.e., hazard ratio between 1.2-1.3) between multidisciplinary program and controls, based on the hazard ratio reported in a study of early palliative care for stage IV lung cancer patients. Based on the above ranges, additional power analysis with a sample of 450 showed that, to reach the power 80% or above, hazard ratio is 1.3 for mortality rate of 30%; hazard ratio of 1.25 for mortality rate of 40%, and hazard ratio of 1.22 for mortality rate of 50%. A higher hazard ratio or higher mortality rate will yield larger statistical power. The sample size is adequate (power >90%) for detecting differences in rates of histologic confirmation of stage and selection of stage-appropriate treatment (20% absolute rate difference).

Statistical analysis

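### Patient FACT-L and HADS have no stated repeated-measures model, baseline adjustment, or rule for deaths and unanswered surveys, so the 3- and 6-month comparisons would by default rest on patients alive and responding

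*Protocol*

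**What the plan says.** - **Endpoint.** The protocol's Study design section lists patient and caregiver quality of life among six endpoints. Overall survival is the primary endpoint (protocol, Length of study; SAP, Statistical Methods (Supplemental)).
- **Collection.** Under Methods or procedures (EFFECTIVENESS), patients complete FACT-L and HADS, and "surveys will be administered up to three times": near first contact, about 3 months later, and about 6 months after baseline.
- **Analysis.** In the Statistical analysis paragraph on self-reported satisfaction and quality of life, summary scores follow each instrument's instructions. Satisfaction is split at 5-6 versus 1-4. The paragraph ends: "Descriptive analysis and logistic model similar to the previous analyses will be used". No cut-point is given for FACT-L or HADS.
- **Response.** Under Benchmarks/Endpoints, the response rate is responses over surveys administered, so a patient who dies before a wave need not enter that wave's denominator.
- **SAP.** It specifies conditional logistic models for binary endpoints and stratified Cox models for survival endpoints, adjusted for age, sex and histology. It names no method for continuous quality-of-life scores. One part of the SAP was not available for this review, so absence there cannot be confirmed.

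**The concern.** A logistic model is not defined for a score without a cut-point, so for FACT-L and HADS what remains in practice is a descriptive comparison at each wave. Descriptive and logistic analyses use whoever has a score. Patients who die, become too ill or stop answering then leave the comparison, and they are unlikely to be a random subset.

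The arms may also lose patients differently. Multidisciplinary patients are approached at their clinic visit, whereas serial-care patients are found through coded lists and treating-group lists. Survey mode may vary between in-person, telephone and mail.

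The baseline and 3-month scores carry information about who is later missing, yet no stated model uses them. At stake is a listed patient-centred endpoint: a difference among responders at 6 months could reflect who was still answering as well as how patients fared.

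**Working it through.** **Inputs (protocol, Sample size calculation).** Stage mix: "about 30% of cases are stage I/II, 30% stage III, and 40% stage IV". Mortality: "The corresponding one year mortality rates are 15%, 30% and 50%, respectively, and two year mortality rate is 30%, 50% and 70% respectively". Planned hazard ratio 1.25.

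**1. Reproduce the plan's own figure.** The protocol says it "estimated the range of the mortality rates from 30% to 50% in our mixed sample with a median follow up of 1.5 years". With constant hazard within stage, mortality at 1.5 years is:
- from the 1-year rates, 1 − (1 − m)^1.5: 0.3 × 21.6% + 0.3 × 41.4% + 0.4 × 64.6% = 44.8%;
- from the 2-year rates, 1 − (1 − m)^0.75: 0.3 × 23.5% + 0.3 × 40.5% + 0.4 × 59.5% = 43.0%.

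Both lie inside 30-50%, so the inputs are coherent.

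**2. Deaths before the later surveys.** At 6 months, 1 − (1 − m)^0.5 gives 7.8%, 16.3% and 29.3% by stage. Weighted: 0.3 × 7.8% + 0.3 × 16.3% + 0.4 × 29.3% = 19.0%.
- Other interpolations give 16.8% (linear), 17.7% (constant hazard from 2-year rates), 18.5% (pooled exponential) and 20.3% (Weibull through both time points).
- At 3 months the same method gives 10.1% (range 9.4-11.9%).

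**3. Deaths by arm.** Take the plan's rates as the serial arm and divide the multidisciplinary hazard by 1.25. The exponent becomes 0.5/1.25 = 0.4, giving 6.3%, 13.3% and 24.2% by stage, or 15.6% overall against 19.0%.

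**4. Bias from death alone.** This was simulated with the same quality-of-life distribution in both arms, the step 3 hazards, and an assumed change in log hazard per SD of quality of life.

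| Assumed log-hazard change per SD | Serial survivors' mean (SD) | Multidisciplinary survivors' mean (SD) | Difference |
|---|---|---|---|
| 0.3 | 0.060 | 0.049 | −0.011 |
| 0.5 | 0.094 | 0.077 | −0.017 |
| 0.8 | 0.137 | 0.115 | −0.023 |

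Survivors score above all enrolled patients in both arms. Most of that cancels in the contrast, and what is left runs against multidisciplinary care.

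**5. Bias from unequal response.** Suppose a latent tendency to respond correlates rho with quality of life. Responders then average rho × phi(z)/keep SD above everyone approached, where keep is the response proportion and z its normal quantile.
- keep = 0.60: 0.644 × rho. keep = 0.80: 0.350 × rho.
- Difference: 0.294 × rho, which is 0.088 SD at rho = 0.3 and 0.147 SD at rho = 0.5, against the better-retained arm with no true effect.
- A simulation that also includes death, with response log-odds rising 0.5 per SD, gives −0.015 SD at 60% v 60%, −0.105 SD at 80% v 60% and −0.152 SD at 90% v 60% (multidisciplinary v serial).

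**6. Scale.** With 19% dead in each arm, about 122 of 150 and 243 of 300 are alive at 6 months. If all answer, the standard error of a mean difference, ignoring matching, is √(1/122 + 1/243) = 0.11 SD. At 80% v 60% response (about 97 and 146 patients) it is √(1/97 + 1/146) = 0.13 SD. Death alone therefore costs at most about a fifth of a standard error (0.023/0.11). The assumed response gap costs about 0.7 to 1.1 (0.088/0.13 to 0.147/0.13).

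**The case against.** **The plan never says it compares survivors only.** True. That is the default consequence of the stated methods, inferred from silence. The logistic sentence may also be meant only for the dichotomised satisfaction scores, and the models it refers back to contain a covariate term, so the baseline score is unmentioned rather than excluded. This limits how the point may be worded. It does not supply a model for FACT-L or HADS.

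**Mortality selection is negligible between arms.** This stands. A reader might infer that survivor selection could pass for a benefit of multidisciplinary care. At the planned hazard ratio, the effect of death is tiny and would hide a benefit.

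**The response figures are not in the documents.** Also true. A reader might take the 60% survey benchmark to mean that 40% non-response in quality of life is accepted. That benchmark is a target for satisfaction responses after contact with the multidisciplinary program. It is not a quality-of-life figure, a 3- or 6-month figure, or a serial-care figure.

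**Mitigation exists.** Telephone and mail fallback, a gift card after the last round, a reported response rate and the survival comparison all help. None of them says how a missing score enters the quality-of-life analysis.

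**Caregiver ratings.** A reader might infer that a usable proxy for the patient is being wasted. The documents do not support this. Caregiver satisfaction is analysed as an outcome in its own right, and the surrogate statistic quoted for the satisfaction instrument is internal consistency, not agreement with the patient.

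**Conclusion.** The point holds as a gap in the analysis of a listed, non-primary endpoint and should be corrected. FACT-L and HADS are measured three times, but the available text has no model suited to the scores, no stated use of baseline or repeated waves, and no rule for death or non-response.

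The 19% dead by 6 months follows from the plan's own rates. It rests on an interpolation and on treating the mortality clock as starting near the baseline survey, which the plan does not state. The bias from death alone depends on the assumed link between quality of life and hazard and is small throughout the range tried. The 0.09-0.15 SD from differential non-response shows what could happen under an assumed 80% v 60% response and a correlation of 0.3-0.5. It is not a forecast. The documents do not establish that the quality-of-life comparison will be biased by a known amount or in favour of multidisciplinary care.

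**What to change.** In the protocol's paragraph on self-reported outcomes and in the SAP:

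- Analyse FACT-L and HADS as continuous scores in a repeated-measures model that uses all available waves, adjusts for the baseline score, and keeps the matching strata (or matching variables) plus age, sex and histology.
- Define the result as quality of life while alive, with no estimate extrapolated beyond death.
- Report deaths and non-response by arm and wave beside it, counting from patients enrolled as well as from surveys administered.

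A composite of being alive with FACT-L no worse than baseline is optional, and only worth adding with a stated rule for living patients who do not respond.

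**Cost.** SAP wording and modest programming, with no new data or visits. The estimand is limited to time alive, and the model corrects for non-response only as far as observed scores and covariates explain it. The baseline survey may follow the first clinic contact, so adjusting for it could remove a small part of any very early effect. The SAP should say so.
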